#### **14.1.1 Overall Summary of TEAEs**

Overall summary of TEAEs will be presented by study period (i.e., Part A, Part B, and Part C) as well as by treatment (including dose level) group. Subjects will be counted only once at the highest severity when summarizing TEAE by severity.

#### **14.1.2 Summary of TEAEs by System Organ Class and Preferred Term**

In addition, TEAEs will be summarized by MedDRA SOC and PT. Each summary table will be presented by study period (i.e., Part A, Part B, and Part C) and treatment (including dose level) group. A subject experiencing multiple occurrences of an adverse event will be counted only once for each PT. Subjects with multiple PTs within a SOC will be counted only once for that SOC. The summaries will be presented for:

- TEAEs by SOC and PT
- TEAEs by Baseline GC dose in HCe ( $\leq 30$  mg/day,  $> 30$  mg/day), SOC, and PT
- Moderate or Severe TEAEs by SOC and PT
- Study drug-related TEAEs by SOC and PT
- Study drug-related TEAEs by GC therapy, SOC, and PT
- AESIs by SOC and PT
- Serious TEAEs by SOC and PT
- Serious study drug-related TEAEs by SOC and PT
- TEAEs leading to study drug discontinuation by SOC and PT
- TEAEs leading to death by SOC and PT

#### **14.2 Clinical Laboratory Evaluation**

Laboratory parameters (hematology, chemistry, lipid panel, thyroid panel, urinalysis, and other tests) will be summarized by treatment (including dose level) and scheduled time point from randomization, based on actual treatment received at each scheduled time point and will include both observed values and change from baseline values.

In addition, the number and percentage of subjects with potentially clinically significant abnormalities (PCSA, see [Table 10](#)) in selected chemistry, hematology, and hormone parameters

(i.e., above the specified upper limit or below the specified limit) will be summarized in shift from baseline tables by scheduled time point.

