2.3.1.2 Testicular

Reversible testicular/spermatocyte degeneration/atrophy was consistently observed in chronic toxicity studies: in rats and dogs dosed with 2000 mg/kg/day (~ 79 -fold [rat] and >200 -fold [dog] higher exposure than the expected average exposure at the highest human dose in this study) for 13 weeks, in rats dosed with ≤ 1000 mg/kg/day (~ 39 -fold higher) for 26 weeks, and in dogs dosed with 1000/500 mg/kg/day (>66 -fold higher) for <20 weeks. Effects included smaller testes and/or epididymides, seminiferous tubule degeneration/atrophy, and germ cell debris and/or reduced sperm in epididymides. However, male reproductive studies in rats showed no impairment in fertility at the highest dose tested (1,000 mg/kg/day [~ 39 -fold higher]). Additionally, no meaningful effects on clinical laboratory markers of testicular function (luteinizing hormone [LH], follicle-stimulating hormone [FSH], inhibin B, and sex hormone-binding globulin [SHBG]) have been observed in male subjects in the Phase 1 or Phase 2 clinical studies.

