2.3.3 Assessment of Potential Risks and Benefits

Multiple study design elements have been incorporated to mitigate the potential risks of LFT laboratory abnormalities, testicular injury, and thyroid effects described in [Section 2.3.1](#). First, these risks are all associated with higher doses of tildacerfont; in this study, tildacerfont tablets will be administered at a range between 50 mg and 200 mg QD, lower than the doses at which elevated LFTs have been observed and doses that have been well tolerated. Additionally, clinical laboratory measures of liver chemistry, testicular function, and thyroid function will be assessed at every study visit in this study. Liver chemistry will be monitored by measuring ALT, AST, alkaline phosphatase (ALP), GGT, total and direct bilirubin, total bile acids, prothrombin time (PT)/international normalized ratio (INR), and partial thromboplastin time (PTT). Testicular function will be monitored by measuring LH, FSH, inhibin B, and SHBG and performing scrotal ultrasounds. Thyroid function will be monitored via a thyroid panel that measures T3, T4, and TSH. Finally, strict individual treatment-stopping criteria for liver chemistry findings and criteria for increased liver chemistry monitoring are in place (see [Section 7.1.1](#) and [Section 13.2](#)).

The reversible histopathological effects of tildacerfont on the male reproductive tract in rat and dog toxicity studies occurred in the context of animals with normal, rather than elevated, baseline hormone function. As a CRF₁ receptor antagonist, tildacerfont is intended to reduce abnormally elevated ACTH and androgen levels. In healthy animal models where baseline hormone levels are within normal ranges, clinical benefits are not expected, and indeed, effects on male reproductive tissues may be expected as a

result of androgen reduction outside of the normal range. However, in patients with CAH, whose baseline ACTH and androgen levels are pathologically elevated, androgen reduction would be considered a positive, therapeutic effect.

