8.2.5 Clinical Laboratory and Urinalysis

Clinical laboratory assessments include hematology, clinical chemistry, coagulation, lipid panel, thyroid panel, LH, FSH, SHBG, renin, aldosterone, inhibin B for males only, and estradiol, prolactin, and progesterone for females only. eGFR for screening will be calculated from blood creatinine measured as part of screening clinical chemistry.

A complete list of study-required clinical laboratory and urinalysis tests is provided in [Section 13.3](#).

All study-required clinical laboratory tests must be conducted in accordance with the laboratory manual and will be performed by a central laboratory.

The Investigator must review the laboratory report, document the review, and record any clinically significant laboratory findings that occur during the study in the AE section of the eCRF. Laboratory reports must be filed with the source documents. Clinically significant laboratory findings are those that are not associated with the underlying disease, unless judged by the Investigator to be more severe than expected for the subject's condition.

All laboratory tests with values considered clinically significantly during the Treatment Period or within 30 days after the last dose of study drug should be reported as AEs and repeated at least weekly until the values return to normal or baseline or are no longer considered clinically significant by the Investigator or Medical Monitor. If such values do not return to normal/baseline within a period of time judged reasonable by the Investigator, the etiology should be identified and the Sponsor notified.

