9.4.6.4 Laboratory Data

Clinical laboratory test results will be listed by subject. Reference ranges provided by the laboratory for each parameter will be used to evaluate the clinical significance of laboratory test results. Values outside the relevant reference range will be flagged in the listings. Abnormal clinical laboratory test results will be listed in a separate listing.

Laboratory data will be summarized in terms of observed values, changes from baseline, values relative to normal ranges, and changes from baseline relative to normal ranges. Subjects meeting specific thresholds for laboratory data will also be summarized as specified the SAP.

P-values for change from baseline and change from placebo or differences in proportions meeting specific thresholds will be derived using t-tests as specified in the SAP.

Additional subgroup analyses based on baseline laboratory data [elevated, normal] will be specified in the SAP.

9.4.6.5 *Vital Signs Data*

Vital signs data will be summarized within appropriately defined categories in terms of observed values (by time point), changes from baseline (by time point), and counts and percentages. Subjects meeting specific thresholds for vital signs data will also be summarized as specified the SAP.

P-values for change from baseline and change from placebo will be derived using t-tests as specified in the SAP.

9.4.6.6 *Electrocardiogram Data*

The QTcF, PR interval, QT interval, QRS duration, and heart rate from standard digital ECGs will be summarized within appropriately defined categories in terms of observed values, changes from baseline, and counts and percentages.

9.4.6.7 *Psychiatric Evaluations*

C-SSRS and HADS data will be listed.

9.4.7 *Baseline Descriptive Statistics*

Demographics and baseline characteristics (including age, sex, race, ethnicity, height, weight, and BMI) will be summarized for the ITT Population.

Biomarkers at screening and at baseline will be summarized for the Safety Population.

Baseline clinical characteristics and history will be summarized.

9.4.8 *Subgroup Analyses*

The following pre-defined subgroups will be analyzed:

- Baseline A4 [≤ 4 x ULN, >4 x ULN]
- Baseline HCe dose [≤ 30 mg/day, >30 mg/day]
- Sex [male, female]
- Age [≤ 30 years, >30 years]; [\leq median, $>$ median]

Any additional subgroup analyses will be specified in the SAP.

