**Table 10 Potentially Clinically Significant Abnormalities by Laboratory Parameter**

Parameter	PCSA Low	PCSA High
Chemistry		
ALT		>3 x ULN
AST		>3 x ULN
ALP		>1.5 x ULN
Total Bilirubin		>1.5 x ULN
Creatinine		> 1.8 mg/dL or > 0.4 mg/dL increase from baseline ( $> 159.16 \mu\text{mol/L}$ or $> 35.37 \mu\text{mol/L}$ increase from baseline)
Sodium	< 130 mEq/L ( $< 130 \text{ mmol/L}$ )	>150 mEq/L ( $> 150 \text{ mmol/L}$ )
Glucose	< 3 mmol/L ( $< 54 \text{ mg/dL}$ )	
Potassium	< 3 mEq/L ( $< 3 \text{ mmol/L}$ )	$\geq 5.5 \text{ mEq/L} (\geq 5.5 \text{ mmol/L})$
Calcium		>11.4 mg/dL ( $> 2.84 \text{ mmol/L}$ )
BUN		> 30 mg/dL and > 10 mg/dL increase from baseline ( $> 10.71 \text{ mmol/L}$ and $> 3.57 \text{ mmol/L}$ increase from baseline)
INR		>1.5 x ULN
Total Bile Acids		>5 x ULN or >3 x ULN if ALT is >3 x ULN
FSH		>15 IU/L if baseline was <5 IU/L
Hematology		
Hemoglobin	$\leq 10 \text{ g/dL}$ and >2 g/dL reduction from baseline ( $\leq 100 \text{ g/L}$ and $> 20 \text{ g/L}$ )	
Leukocytes	<500/ $\mu\text{L}$ ( $< 0.5 \times 10^9/\text{L}$ )	
Neutrophils	<1800/ $\mu\text{L}$ and >500/ $\mu\text{L}$ reduction from baseline	
Platelets	<50,000/ $\mu\text{L}$ ( $< 50 \times 10^9/\text{L}$ )	

All laboratory results will be listed with reference ranges and range indicator (Low, High). In addition, laboratory results that meet or exceed the pre-specified PCSA levels ([Table 10](#)) will be flagged.

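### SAP 14.2 plans no by-sex summary of LH, FSH and SHBG, its one FSH abnormality criterion cannot be met from a baseline of 5 IU/L or more, and the protocol's normal-range summaries are not carried forward

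*SAP*

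**What the plan says.** Protocol 2.3.1.2 gives the origin of the risk: "Reversible testicular/spermatocyte degeneration/atrophy was consistently observed in chronic toxicity studies". Protocol 2.3.3 gives the mitigation: "Testicular function will be monitored by measuring LH, FSH, inhibin B, and SHBG and performing scrotal ultrasounds". Protocol 8.2.5 lists LH, FSH and SHBG for every subject and limits other assays by sex: "inhibin B for males only, and estradiol, prolactin, and progesterone for females only". Inhibin B is therefore the only one of the four laboratory markers that is male-only by construction.

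SAP 14.2 says laboratory parameters "will be summarized by treatment (including dose level) and scheduled time point from randomization, based on actual treatment received at each scheduled time point", as observed values and changes from baseline. It adds shift tables for potentially clinically significant abnormalities (PCSAs) as defined in Table 10. Among the four testicular markers, Table 10 has a row only for FSH, with the high criterion ">15 IU/L if baseline was <5 IU/L" and no restriction by sex. LH, SHBG, inhibin B and the thyroid panel have no row.

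Protocol 9.4.6.4 plans laboratory summaries that also include "values relative to normal ranges, and changes from baseline relative to normal ranges". SAP 14.2 does not mention these, and SAP Section 15 does not list a change.

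**The concern.** The laboratory tables are where a dose-related effect on the testis would be compared with placebo. Three of the four markers also vary in women for reasons unrelated to the testis; Protocol 5.2.5.2 itself refers to a postmenopausal FSH range. A table that pools the sexes does not describe men. Elsewhere the SAP states a sex split where it wants one: A4 limits in Table 4, cardiovascular criteria in Table 6 and QTcF thresholds in Table 12. For these three hormones it states none.

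Other sources of group-level evidence are thin. Follow-up scrotal ultrasound is done only in men who had a testicular adrenal rest tumour at baseline (Protocol 1.3.3, footnotes), and placebo control lasts only the 12 weeks of Part A. What is at stake is whether the report can show, by dose, what happened to these hormones in men.

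**Working it through.** **1. Design figure.** Protocol 9.2 gives 15 per group and 15% dropout: 15 / 0.85 = 17.6, rounded up to 18; 18 × 4 = 72. Both stated figures reproduce, and 18 per arm is used below. The documents give no sex split and no SDs for these hormones, so those are assumptions shown as ranges.

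**2. Dilution of the mean.** Let p be the male share and d the true shift in men, with no shift in women. The pooled mean shift is p × d, whatever the SDs. At p = 0.5 and d = 1.5 male SDs, this is 0.5 × 1.5 = 0.75.

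**3. Added variation.** Set the male SD of change to 1 and the female SD to k, with n = 18 per arm and m men per arm (p = m/18).
- Men only: power = Φ(d / √(2/m) − 1.96).
- Pooled: V_placebo = p + (1 − p)k²; V_active = V_placebo + p(1 − p)d²; SE = √((V_active + V_placebo)/18); power = Φ(pd/SE − 1.96).

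Example with m = 9, d = 1.5, k = 2:
- Men only: 1.5 / √(2/9) = 3.18; Φ(1.22) = 89%.
- Pooled: V_placebo = 0.5 + 0.5 × 4 = 2.5; V_active = 2.5 + 0.25 × 2.25 = 3.0625; SE = √(5.5625/18) = 0.556; Φ(0.75/0.556 − 1.96) = Φ(−0.61) = 27%.

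| Men per arm | d | Pooled shift | Men only | Pooled, k = 1 / 2 / 3 |
|---|---|---|---|---|
| 5 | 1.5 | 0.42 | 66% | 20 / 10 / 7% |
| 7 | 1.5 | 0.58 | 80% | 34 / 17 / 10% |
| 9 | 1.5 | 0.75 | 89% | 51 / 27 / 16% |
| 11 | 1.5 | 0.92 | 94% | 69 / 42 / 26% |
| 5 | 1.0 | 0.28 | 35% | 12 / 7 / 5% |
| 9 | 1.0 | 0.50 | 56% | 29 / 15 / 10% |
| 11 | 1.0 | 0.61 | 65% | 41 / 23 / 14% |

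The ordering is stable, but the levels depend heavily on the assumed effect and SDs. In FSH units, at 50% men and using the t distribution, a +3 IU/L shift with male SD 1.5–2 and female SD 4–8 gives 85–98% in men alone and 11–28% pooled. With both SDs equal to 2, pooled power is 49%. With a +1.5 IU/L shift, men-only power is only 32–51%.

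**4. Imbalance.** Randomisation is stratified by A4 only (Protocol 6.3). With a male share of 30–60%, two arms of 18 differ by four or more men with probability 20–24%. That would also distort pooled means of observed values.

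**5. FSH criterion, evaluated directly** (value above 15 and baseline below 5):

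| Baseline to value (IU/L) | Ratio | Criterion met |
|---|---|---|
| 4.9 to 15.1 | 3.1 | yes |
| 5.0 to 15.1 | 3.0 | no |
| 5.0 to 30 | 6.0 | no |
| 8 to 40 | 5.0 | no |
| 2.0 to 14.9 | 7.5 | no |

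No value, however high, meets it once baseline is 5 IU/L or more.

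**6. Normal-range summaries.** Protocol 9.4.6.4 lists four elements: observed values, changes from baseline, values relative to normal ranges, and changes relative to normal ranges. SAP 14.2 states the first two. Its shift tables use Table 10 limits, which do not cover LH, SHBG, inhibin B or the thyroid panel. The last two elements therefore have no counterpart in SAP 14.2 for these tests.

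**The case against.** The strongest reply is that individual signals are not hidden. Directly below Table 10 the SAP states: "All laboratory results will be listed with reference ranges and range indicator (Low, High". Protocol 9.4.6.4 adds flags for out-of-range values and a separate listing of abnormal results. Protocol 7.1.6 has investigators assess reproductive-hormone changes in each subject, and an independent board reviews unblinded safety data. This stands. A reader might infer that FSH is the only flag, or that a testicular signal would be missed; the documents support neither. What the listings and case review do not provide is a by-dose comparison in men.

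Second, pooling is inferred from silence. Table layouts are in mock-shells that are not part of these documents, and SAP 10.7 allows forest plots by sex for selected safety evaluations that it does not name. Either could supply the split, but the SAP commits to neither for these hormones.

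Third, a reader might infer that the SAP withdrew the normal-range summaries. It does not say so: the PCSA tables are introduced as an addition. The SAP governs where the two documents are inconsistent (SAP Section 4), and silence is not clearly inconsistency. It is an omission that needs reconciling.

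Fourth, counting women under the FSH criterion is not shown to be an error, because Protocol 7.1.6 treats LH, FSH and SHBG changes as safety signals without limiting them to men. Finally, the testicular finding is nonclinical and reversible, at about 39-fold or higher exposure, with no meaningful effect on these markers in male subjects so far (Protocol 2.3.1.2). That tempers the urgency.

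**Conclusion.** The point holds as a reporting gap in descriptive safety tables. Followed as written, SAP 14.2 shrinks a male-only shift in LH, FSH or SHBG to the male share of that shift and adds female variation. The size of the shrinkage follows from the male share alone, which the documents do not give; one half is the 50% case. Inhibin B is not diluted, but it has no PCSA criterion. The FSH gap at a baseline of 5 IU/L or more needs no assumptions, and its consequence is absence from the PCSA shift tables, not from the listings. The missing normal-range summaries are an unreconciled difference between protocol and SAP.

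The power figures should not be quoted as the size of the problem. The sex split, SDs and effect are assumed. SAP 14.2 specifies no test for these hormones, although Protocol 9.4.6.4 refers to t-tests to be specified in the SAP. They show only that splitting by sex helps under every assumption tried.

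**What to change.** - In SAP 14.2, present observed values and changes from baseline in LH, FSH and SHBG separately for men and women within treatment group.
- Present the FSH PCSA counts by sex. Ask the sponsor's clinical experts to reconsider the criterion so that subjects with a baseline of 5 IU/L or more are covered; the cut-off is theirs to choose.
- Reconcile SAP 14.2 with Protocol 9.4.6.4: either include normal-range shift summaries for LH, FSH, SHBG, inhibin B and the thyroid panel, using the laboratory's sex-specific ranges, or record the change in Section 15.
- If the mock-shells already split these hormones by sex, say so in SAP 14.2.

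The cost is extra tables with smaller denominators, about 5 to 11 men per arm for a male share of 30–60%. No new data are needed.

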7.1.1 Liver Chemistry Stopping Criteria

Liver chemistry stopping criteria defined in [Table 3](#) are designed to ensure subject safety and to evaluate liver event etiology. The Investigator should notify the Sponsor within 24 hours of awareness if any of the criteria defined in [Table 3](#) are met. Further suggested actions, follow-up assessments, and monitoring assessments are provided in [Section 13.2](#). A significant change in liver chemistry that requires increased monitoring but does not necessarily satisfy stopping criteria may still be considered an adverse event of special interest (AESI) (see [Section 8.3.8](#)).

Table 3. Stopping Criteria and Increased Monitoring for Liver Chemistry Elevations

Criteria	Actions	
ALT \geq 5x ULN	Discontinue study drug and notify Sponsor.	
ALT \geq 3x ULN	AND total bilirubin \geq 2x ULN (>35% direct bilirubin) ¹	Discontinue study drug and notify Sponsor. Possible Hy's Law case— report as SAE .
	AND INR >1.5	Discontinue study drug and notify Sponsor. Possible Hy's Law case— report as SAE .
	AND subject has symptoms (new or worsening) believed to be related to liver injury or hypersensitivity ²	Discontinue study drug and notify Sponsor.
	AND total bile acids >3x ULN	Withhold study drug and notify Sponsor. Repeat liver chemistry tests after 1 week, and discuss with Medical Monitor whether to discontinue study drug.
	ALT \geq 3x ULN only	Monitor weekly for 4 weeks while continuing study drug and notify Sponsor (see Section 13.2.2)
	AND cannot be monitored weekly for 4 weeks	Discontinue study drug and notify Sponsor.
	persists for \geq 4 weeks	Discontinue study drug and notify Sponsor.

Abbreviations: ALT, alanine aminotransferase; INR, international normalized ratio; SAE, serious adverse event; ULN, upper limit of normal.

¹ If serum bilirubin fractionation is not immediately available, discontinue study drug if ALT \geq 3x ULN and bilirubin \geq 2x ULN and record the presence/absence of detectable urinary bilirubin on dipstick, which is indicative of direct bilirubin elevations suggesting liver injury.

² Symptoms related to liver injury include fatigue, nausea, vomiting, right upper quadrant pain or tenderness, and jaundice. Symptoms related to hypersensitivity include fever, rash, and eosinophilia.

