13.2.1.3 Monitoring

For a possible Hy's Law case (ALT \geq 3x ULN AND total bilirubin \geq 2x ULN or INR $>$ 1.5):

- Repeat liver chemistry tests (include ALT, AST, ALP, GGT, bilirubin, total bile acids, PT/INR, and PTT) and perform liver event follow-up assessments within **24 hours**.
- Collect blood samples twice weekly for repeat liver chemistry tests (ALT, AST, ALP, GGT, bilirubin, total bile acids, PT/INR, and PTT) until abnormalities resolve, stabilize, or return to baseline.
- A specialist or hepatology consultation is recommended.

For a non-Hy's Law case of ALT \geq 3x ULN that meets other liver chemistry stopping criteria:

- Repeat liver chemistry tests (include ALT, AST, ALP, GGT, bilirubin, total bile acids, PT/INR, and PTT) and perform liver event follow-up assessments within 24 to 72 hours.
- Collect blood samples weekly for repeat liver chemistry tests (ALT, AST, ALP, GGT, bilirubin, total bile acids, PT/INR, and PTT) until abnormalities resolve, stabilize, or return to baseline.

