13.2.2 Increased Liver Chemistry Monitoring While Continuing Study Drug

If ALT \geq 3x ULN and $<$ 5x ULN **and** total bilirubin $<$ 2x ULN, **without** symptoms believed to be related to liver injury or hypersensitivity, **and** the subject can be monitored weekly for 4 weeks, perform the following actions:

- Notify the Medical Monitor within **24 hours** of learning of the abnormality to discuss subject safety.
- Subject can continue study drug.

- Collect blood samples weekly for repeat liver chemistry tests (ALT, AST, ALP, GGT, bilirubin, total bile acids, PT/INR, and PTT) until the abnormalities resolve, stabilize, or return to baseline.
- If at any time the subject meets liver chemistry stopping criteria, proceed as described in [Section 7.1.1](#) and [Section 13.2.1](#).
- If, after 4 weeks of monitoring, ALT <3x ULN and total bilirubin <2x ULN, monitor per standard scheduling for remainder of study and follow-up period.

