## 9.4 Analysis Windows

Analysis visits will match the protocol-specified visits (Screening, Day 1, Week 4, etc.). Unscheduled clinical visits may be used to capture missed or partially completed clinical visits; therefore, analysis visits and their windows are defined using Study Day (See [Section 9.3.2](#)). For the purposes of data analysis and summary, assessments and/or measurements, the protocol-specified visit will be preferentially flagged for analysis. In the absence of a protocol-specified visit, the analysis flag will be based on the collection date/time that is closest to the protocol-scheduled time point (or target Study Day). Analysis visit windows are presented in [Table 9](#).

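### SAP 14.2 and Table 10 do not report the protocol's own liver criteria: the INR limit differs, the Hy's Law pairs and ALT ≥5x ULN are not counted, and off-schedule peaks can be left out of the tables

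*SAP*

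**What the plan says.** **Protocol.** Table 3 (section 7.1.1) acts on ALT ≥5x ULN alone. It also acts on ALT ≥3x ULN combined with any of: total bilirubin ≥2x ULN, INR above 1.5 (an absolute value), symptoms, or total bile acids above 3x ULN. The bilirubin and INR pairs are possible Hy's Law cases, to be reported as SAEs; section 13.3 repeats this.

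Follow-up sampling is off schedule. Section 13.2.2, for isolated ALT elevations on continued drug, says "Collect blood samples weekly for repeat liver chemistry tests". Section 13.2.1.3, for possible Hy's Law cases, says "Collect blood samples twice weekly for repeat liver chemistry tests".

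Protocol 9.4.6.4 leaves the laboratory thresholds to the SAP: "Subjects meeting specific thresholds for laboratory data will also be summarized as specified the SAP".

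**SAP.** Table 10 has separate rows for ALT >3x, AST >3x, ALP >1.5x, total bilirubin >1.5x and INR >1.5x ULN. One row combines parameters, total bile acids: ">5 x ULN or >3 x ULN if ALT is >3 x ULN". Subjects meeting these limits "will be summarized in shift from baseline tables by scheduled time point". Under section 9.4, "the protocol-specified visit will be preferentially flagged for analysis"; an unscheduled value is used only when the scheduled one is absent. The laboratory listings carry all results and flag those at Table 10 levels.

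**The concern.** Protocol 2.3.3 names liver function test elevation as the observed risk to be monitored and presents the liver stopping criteria as part of the mitigation. In a dose-ranging trial, a reader of the report will want to know how many subjects on placebo, 50, 100 and 200 mg met each of those criteria. The SAP's laboratory tables use different limits, do not link results within a subject for the two possible Hy's Law pairs, and draw on scheduled visits while the protocol sends liver follow-up between visits. A subject who met a protocol criterion may therefore not be recognisable as such in the laboratory summaries.

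**Working it through.** The plan states no figure to reproduce. The check compares limits and timing rules.

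**1. INR limit.** The protocol limit is 1.5. The SAP limit is 1.5 x ULN. The documents give no INR ULN, so a range is assumed:

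| Assumed ULN | SAP limit | Difference from 1.5 |
|---|---|---|
| 0.9 | 1.35 | −0.15 |
| 1.0 | 1.50 | 0 |
| 1.1 | 1.65 | +0.15 |
| 1.2 | 1.80 | +0.30 |
| 1.3 | 1.95 | +0.45 |

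The SAP is looser only when the ULN exceeds 1.0.

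**2. Combinations.** Illustrative cases run through both documents, with each value at a scheduled visit:

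| Case | Protocol Table 3 | SAP Table 10 rows met |
|---|---|---|
| ALT 5.5x | ALT ≥5x | ALT, counted only as >3x |
| ALT 3.5x, bilirubin 2.2x | Possible Hy's Law | ALT and bilirubin, in two unlinked rows |
| ALT 3.5x, INR 1.6 | Possible Hy's Law | ALT; INR at ULN 1.0, but not at 1.1 or 1.2 |
| ALT 3.0x, bilirubin 2.0x | Possible Hy's Law if the direct-bilirubin condition is met | Bilirubin only |
| ALT 3.5x, bile acids 4x | ALT with bile acids | ALT, and the combined bile acids row |

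The fourth case turns on ≥3x in the protocol against >3x in the SAP, and matters only at exactly 3.0x. The bilirubin row (>1.5x) is more sensitive than the protocol's 2x.

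**3. Timing.** Scheduled laboratory days from Week 6 to Week 76 are 43, 71, 99, 127, 169, 211, 267, 323, 407, 491 and 533. The gaps are 28, 28, 28, 42, 42, 56, 56, 84, 84 and 42 days, or 4 to 12 weeks. A gap of w weeks leaves w − 1 weekly dates strictly between visits, so 3 to 11.

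Take an isolated ALT elevation at Week 10 (Day 71), retested weekly for four weeks on Days 78, 85, 92 and 99. Day 99 is the scheduled Week 14 visit. Of the five results, 3 are unscheduled (Days 78, 85 and 92). A trigger on Day 99 gives the same count, ending on Day 127. If the scheduled samples exist, those three do not enter the by-visit tables, and the SAP plans no worst-on-treatment count that would pick them up.

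**4. Week 6 window.** SAP Table 9 assigns Days 37 to 57 to Week 6 (target Day 43), and Week 10 starts on Day 58. For a subject randomised and first dosed on Day 43, an unscheduled sample on Days 44 to 57 is on treatment but maps to Week 6. It therefore enters no post-baseline count. SAP 9.3.10 protects the baseline value itself, because for these parameters baseline is the last non-missing result before the first double-blind dose.

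**The case against.** The strongest reply is that these cases are reported elsewhere. A reader might infer that liver cases can be missing from the safety results altogether. The documents do not support that:

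- Possible Hy's Law cases must be reported as SAEs (protocol Table 3 and 13.3).
- A test result that leads to discontinuation is an AE (protocol 8.3.1).
- SAP 14.1 lists SAEs, AESIs and discontinuations separately, and 14.1.2 tabulates them by part and dose.
- Every laboratory result is listed, with flags.
- A DSMB that includes a hepatologist reviews unblinded safety data (protocol 10.6).

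All of this stands. It does not fill the gap, because those tables count by system organ class and preferred term, which does not give the number of subjects meeting each Table 3 category. The listing flags also carry the SAP's INR limit. The AESI route is uncertain as well: protocol 13.2.1.1 marks stopping-rule liver events as AESIs, while 8.3.8 describes liver AESIs as changes that do not satisfy the stopping rules. Those two passages need reconciling.

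A reader might also infer that the SAP never combines parameters. It does, for bile acids with ALT. Nor does a looser INR limit make a case vanish: ALT above 3x at a scheduled visit is counted in the ALT row whatever the INR.

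Finally, Table 10 sets reporting flags, not stopping rules, and the protocol allows the SAP to choose them. That is correct, and it is why the request is to reconcile the limits and add a table. The ALT boundary is a small matter, and the SAP's wording for listing flags (meeting or exceeding the level) may already cover it there.

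**Conclusion.** The point holds as a reporting gap in the laboratory summary tables. It is not a failure to capture or report liver cases.

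Three parts follow directly from the documents. The INR definitions differ. No table counts ALT with bilirubin, ALT with INR, or ALT ≥5x ULN. The counts are by scheduled time point, so off-schedule peaks can be absent, as can unscheduled results on Days 44 to 57.

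The size is conditional. The INR gap of 0.15 to 0.30 rests on an assumed ULN of 1.1 to 1.2 and disappears at 1.0. The 3-of-5 figure applies to a trigger at Week 10 or Week 14 with weekly retests kept on time and the scheduled samples present. How often a peak would fall between visits cannot be estimated from the documents. They also do not show that the dose comparison would in fact be understated, only that the planned tables cannot supply it for the protocol's own criteria.

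**What to change.** - Reconcile the INR definition (absolute or multiple of ULN) and the ALT boundary (≥ or >) between protocol Table 3 and SAP Table 10, and state the reason for any difference that is kept. This review does not say which clinical limit is right.
- Add to SAP 14.2 one subject-level table, by dose and by study part, of the worst value after the first double-blind dose from all scheduled and unscheduled samples. Use the protocol's Table 3 laboratory categories: ALT ≥3x, ALT ≥5x, and ALT ≥3x with bilirubin, with INR and with bile acids.
- State in SAP 9.4 that a sample taken after the first double-blind dose is not assigned to the Week 6 baseline visit.

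The cost is a few lines of SAP text and one extra table from data already collected. No new sampling and no change to any clinical rule is needed.
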